## **Post 2nd injection**

- Indirect Ophthalmoscopy (SE) – 1 to 2 minutes after the second injection to assure that the optic nerve is perfused.

- Ophthalmologic exam/Tonometry (SE) – At least 30 minutes after the second injection, a full ophthalmologic exam must be performed and IOP must be < 30 mmHg before the subject leaves the clinic.

### **3-Day Post-Injection Safety Check (± 1 day)**

- Telephone call to subject to ensure there are no signs or symptoms of retinal detachment or endophthalmitis.

### **10.2.11 Month 5 Visit (± 7 days)**

#### **Pre-injection**

- Protocol refraction and visual acuity (4 meters) using ETDRS chart (SE)
- Tonometry and ophthalmologic examination (SE)

#### **Injection**

- 1st Injection - Randomized Treatment
  - Indirect Ophthalmoscopy (SE) – 1 to 2 minutes after the injection to assure that the optic nerve is perfused.
  - Tonometry (SE) – After the injection, IOP must be ≤ 21 mmHg or within 5 mmHg of pre-injection before the 2nd injection can be given.
- 2nd Injection - Randomized Treatment

#### **Post 2nd injection**

- Indirect Ophthalmoscopy (SE) – 1 to 2 minutes after the second injection to assure that the optic nerve is perfused.
- Ophthalmologic exam/Tonometry (SE) – At least 30 minutes after the second injection, a full ophthalmologic exam must be performed and IOP must be < 30 mmHg before the subject leaves the clinic.

### **3-Day Post-Injection Safety Check (± 1 day)**

- Telephone call to subject to ensure there are no signs or symptoms of retinal detachment or endophthalmitis.

### **10.2.12 Month 6 Visit (± 7 days)**

#### **Pre-injection**

- Protocol refraction and visual acuity (4 meters) using ETDRS chart (OU)
- Ophthalmologic examination and Goldmann applanation tonometry (OU)
- Spectral Domain Optical Coherence Tomography (SD-OCT) (OU)

- Fundus Autofluorescence (FAF) (OU)
- Vital signs
- Serum pregnancy test (if applicable)

### **Injection**

- 1st Injection - Randomized Treatment
  - Indirect Ophthalmoscopy (SE) – 1 to 2 minutes after the injection to assure that the optic nerve is perfused.
  - Tonometry (SE) – After the injection, IOP must be  $\leq 21$  mmHg or within 5 mmHg of pre-injection before the 2nd injection can be given.
- 2nd Injection - Randomized Treatment

### **Post 2nd injection**

- Indirect Ophthalmoscopy (SE) – 1 to 2 minutes after the second injection to assure that the optic nerve is perfused.
- Ophthalmologic exam/Tonometry (SE) – At least 30 minutes after the second injection, a full ophthalmologic exam must be performed and IOP must be  $< 30$  mmHg before the subject leaves the clinic.

### **3-Day Post-Injection Safety Check ( $\pm 1$ day)**

- Telephone call to subject to ensure there are no signs or symptoms of retinal detachment or endophthalmitis.

### **10.2.13 Month 7 Visit ( $\pm 7$ days)**

#### **Pre-injection**

- Protocol refraction and visual acuity (4 meters) using ETDRS chart (SE)
- Tonometry and ophthalmologic examination (SE)

#### **Injection**

- 1st Injection - Randomized Treatment
  - Indirect Ophthalmoscopy (SE) – 1 to 2 minutes after the injection to assure that the optic nerve is perfused.
  - Tonometry (SE) – After the injection, IOP must be  $\leq 21$  mmHg or within 5 mmHg of pre-injection before the 2nd injection can be given.
- 2nd Injection - Randomized Treatment

### **Post 2nd injection**

- Indirect Ophthalmoscopy (SE) – 1 to 2 minutes after the second injection to assure that the optic nerve is perfused.
- Ophthalmologic exam/Tonometry (SE) – At least 30 minutes after the second injection, a full ophthalmologic exam must be performed and IOP must be < 30 mmHg before the subject leaves the clinic.

### **3-Day Post-Injection Safety Check (± 1 day)**

- Telephone call to subject to ensure there are no signs or symptoms of retinal detachment or endophthalmitis.

### **10.2.14 Month 8 Visit (± 7 days)**

#### **Pre-injection**

- Protocol refraction and visual acuity (4 meters) using ETDRS chart (SE)
- Tonometry and ophthalmologic examination (SE)

#### **Injection**

- 1st Injection - Randomized Treatment
  - Indirect Ophthalmoscopy (SE) – 1 to 2 minutes after the injection to assure that the optic nerve is perfused.
  - Tonometry (SE) – After the injection, IOP must be ≤ 21 mmHg or within 5 mmHg of pre-injection before the 2nd injection can be given.
- 2nd Injection - Randomized Treatment

### **Post 2nd injection**

- Indirect Ophthalmoscopy (SE) – 1 to 2 minutes after the second injection to assure that the optic nerve is perfused.
- Ophthalmologic exam/Tonometry (SE) – At least 30 minutes after the second injection, a full ophthalmologic exam must be performed and IOP must be < 30 mmHg before the subject leaves the clinic.

### **3-Day Post-Injection Safety Check (± 1 day)**

- Telephone call to subject to ensure there are no signs or symptoms of retinal detachment or endophthalmitis.

### **10.2.15 Month 9 Visit ( $\pm$ 7 days)**

#### **Pre-injection**

- Protocol refraction and visual acuity (4 meters) using ETDRS chart (OU)
- Goldmann applanation tonometry and ophthalmologic examination (OU)
- Color fundus photography (FP) (OU)
- Fluorescein Angiography (FA) (OU, transit study eye)
- Spectral Domain Optical Coherence Tomography (SD-OCT) (OU)
- Fundus Autofluorescence (FAF) (OU)
- Microperimetry testing (OU) (optional assessment)

#### **Injection**

- 1st Injection - Randomized Treatment
  - Indirect Ophthalmoscopy (SE) – 1 to 2 minutes after the injection to assure that the optic nerve is perfused.
  - Tonometry (SE) – After the injection, IOP must be  $\leq$  21 mmHg or within 5 mmHg of pre-injection before the 2nd injection can be given.
- 2nd Injection - Randomized Treatment

#### **Post 2nd injection**

- Indirect Ophthalmoscopy (SE) – 1 to 2 minutes after the second injection to assure that the optic nerve is perfused.
- Ophthalmologic Exam/Tonometry (SE) – At least 30 minutes after the second injection, a full ophthalmologic exam must be performed and IOP must be  $<$  30 mmHg before the subject leaves the clinic.

#### **3-Day Post-Injection Safety Check ( $\pm$ 1 day)**

- Telephone call to subject to ensure there are no signs or symptoms of retinal detachment or endophthalmitis.

### **10.2.16 Month 10 Visit ( $\pm$ 7 days)**

#### **Pre-injection**

- Protocol refraction and visual acuity (4 meters) using ETDRS chart (SE)
- Tonometry and ophthalmologic examination (SE)

## **Injection**

- 1st Injection - Randomized Treatment
  - Indirect Ophthalmoscopy (SE) – 1 to 2 minutes after the injection to assure that the optic nerve is perfused.
  - Tonometry (SE) – After the injection, IOP must be  $\leq 21$  mmHg or within 5 mmHg of pre-injection before the 2nd injection can be given.
- 2nd Injection - Randomized Treatment

## **Post 2nd injection**

- Indirect Ophthalmoscopy (SE) – 1 to 2 minutes after the second injection to assure that the optic nerve is perfused.
- Ophthalmologic exam/Tonometry (SE) – At least 30 minutes after the second injection, a full ophthalmologic exam must be performed and IOP must be  $< 30$  mmHg before the subject leaves the clinic.

## **3-Day Post-Injection Safety Check ( $\pm 1$ day)**

- Telephone call to subject to ensure there are no signs or symptoms of retinal detachment or endophthalmitis.

## **10.2.17 Month 11 Visit ( $\pm 7$ days)**

### **Pre-injection**

- Protocol refraction and visual acuity (4 meters) using ETDRS chart (SE)
- Tonometry and ophthalmologic examination (SE)

## **Injection**

- 1st Injection - Randomized Treatment
  - Indirect Ophthalmoscopy (SE) – 1 to 2 minutes after the injection to assure that the optic nerve is perfused.
  - Tonometry (SE) – After the injection, IOP must be  $\leq 21$  mmHg or within 5 mmHg of pre-injection before the 2nd injection can be given.
- 2nd Injection - Randomized Treatment

## **Post 2nd injection**

- Indirect Ophthalmoscopy (SE) – 1 to 2 minutes after the second injection to assure that the optic nerve is perfused.

- Ophthalmologic exam/Tonometry (SE) – At least 30 minutes after the second injection, a full ophthalmologic exam must be performed and IOP must be < 30 mmHg before the subject leaves the clinic.

### **3-Day Post-Injection Safety Check (± 1 day)**

- Telephone call to subject to ensure there are no signs or symptoms of retinal detachment or endophthalmitis.

### **10.2.18 Month 12 Visit (± 7 days)**

#### **Pre-injection**

- Protocol refraction and visual acuity (4 meters) using ETDRS chart (OU)
- Tonometry and ophthalmologic examination (OU)
- Spectral Domain Optical Coherence Tomography (SD-OCT) (OU)
- Fundus Autofluorescence (FAF) (OU)
- Vital signs
- Serum pregnancy test (if applicable)

#### **Injection**

- 1st Injection - Randomized Treatment
  - Indirect Ophthalmoscopy (SE) – 1 to 2 minutes after the injection to assure that the optic nerve is perfused.
  - Tonometry (SE) – After the injection, IOP must be ≤ 21 mmHg or within 5 mmHg of pre-injection before the 2nd injection can be given.
- 2nd Injection - Randomized Treatment

#### **Post 2nd injection**

- Indirect Ophthalmoscopy (SE) – 1 to 2 minutes after the second injection to assure that the optic nerve is perfused.
- Ophthalmologic exam/Tonometry (SE) – At least 30 minutes after the second injection, a full ophthalmologic exam must be performed and IOP must be < 30 mmHg before the subject leaves the clinic.

### **3-Day Post-Injection Safety Check ( $\pm$ 1 day)**

- Telephone call to subject to ensure there are no signs or symptoms of retinal detachment or endophthalmitis.

### **10.2.19 Month 13 Visit ( $\pm$ 7 days)**

#### **Pre-injection**

- Protocol refraction and visual acuity (4 meters) using ETDRS chart (SE)
- Tonometry and ophthalmologic examination (SE)

#### **Injection**

- 1st Injection - Randomized Treatment
  - Indirect Ophthalmoscopy (SE) – 1 to 2 minutes after the injection to assure that the optic nerve is perfused.
  - Tonometry (SE) – After the injection, IOP must be  $\leq$  21 mmHg or within 5 mmHg of pre-injection before the 2nd injection can be given.
- 2nd Injection - Randomized Treatment

#### **Post 2nd injection**

- Indirect Ophthalmoscopy (SE) – 1 to 2 minutes after the second injection to assure that the optic nerve is perfused.
- Ophthalmologic exam/Tonometry (SE) – At least 30 minutes after the second injection, a full ophthalmologic exam must be performed and IOP must be  $<$  30 mmHg before the subject leaves the clinic.

### **3-Day Post-Injection Safety Check ( $\pm$ 1 day)**

- Telephone call to subject to ensure there are no signs or symptoms of retinal detachment or endophthalmitis.

### **10.2.20 Month 14 Visit ( $\pm$ 7 days)**

#### **Pre-injection**

- Protocol refraction and visual acuity (4 meters) using ETDRS chart (SE)
- Tonometry and ophthalmologic examination (SE)

#### **Injection**

- 1st Injection - Randomized Treatment
  - Indirect Ophthalmoscopy (SE) – 1 to 2 minutes after the injection to assure that the optic nerve is perfused.

- Tonometry (SE) – After the injection, IOP must be  $\leq 21$  mmHg or within 5 mmHg of pre-injection before the 2nd injection can be given.

- 2nd Injection - Randomized Treatment

### **Post 2nd injection**

- Indirect Ophthalmoscopy (SE) – 1 to 2 minutes after the second injection to assure that the optic nerve is perfused.
- Ophthalmologic exam/Tonometry (SE) – At least 30 minutes after the second injection, a full ophthalmologic exam must be performed and IOP must be  $< 30$  mmHg before the subject leaves the clinic.

### **3-Day Post-Injection Safety Check ( $\pm 1$ day)**

- Telephone call to subject to ensure there are no signs or symptoms of retinal detachment or endophthalmitis.

## **10.2.21 Month 15 Visit ( $\pm 7$ days)**

### **Pre-injection**

- Protocol refraction and visual acuity (4 meters) using ETDRS chart (SE)
- Tonometry and ophthalmologic examination (SE)
- Spectral Domain Optical Coherence Tomography (SD-OCT) (OU)
- Fundus Autofluorescence (FAF) (OU)

### **Injection**

- 1st Injection - Randomized Treatment
  - Indirect Ophthalmoscopy (SE) – 1 to 2 minutes after the injection to assure that the optic nerve is perfused.
  - Tonometry (SE) – After the injection, IOP must be  $\leq 21$  mmHg or within 5 mmHg of pre-injection before the 2nd injection can be given.
- 2nd Injection - Randomized Treatment

### **Post 2nd injection**

- Indirect Ophthalmoscopy (SE) – 1 to 2 minutes after the second injection to assure that the optic nerve is perfused.
- Ophthalmologic exam/Tonometry (SE) – At least 30 minutes after the second injection, a full ophthalmologic exam must be performed and IOP must be  $< 30$  mmHg before the subject leaves the clinic.

### **3-Day Post-Injection Safety Check ( $\pm$ 1 day)**

- Telephone call to subject to ensure there are no signs or symptoms of retinal detachment or endophthalmitis.

### **10.2.22 Month 16 Visit ( $\pm$ 7 days)**

#### **Pre-injection**

- Protocol refraction and visual acuity (4 meters) using ETDRS chart (SE)
- Tonometry and ophthalmologic examination (SE)

#### **Injection**

- 1st Injection - Randomized Treatment
  - Indirect Ophthalmoscopy (SE) – 1 to 2 minutes after the injection to assure that the optic nerve is perfused.
  - Tonometry (SE) – After the injection, IOP must be  $\leq$  21 mmHg or within 5 mmHg of pre-injection before the 2nd injection can be given.
- 2nd Injection - Randomized Treatment

#### **Post 2nd injection**

- Indirect Ophthalmoscopy (SE) – 1 to 2 minutes after the second injection to assure that the optic nerve is perfused.
- Ophthalmologic exam/Tonometry (SE) – At least 30 minutes after the second injection, a full ophthalmologic exam must be performed and IOP must be  $<$  30 mmHg before the subject leaves the clinic.

### **3-Day Post-Injection Safety Check ( $\pm$ 1 day)**

- Telephone call to subject to ensure there are no signs or symptoms of retinal detachment or endophthalmitis.

### **10.2.23 Month 17 Visit ( $\pm$ 7 days)**

#### **Pre-injection**

- Protocol refraction and visual acuity (4 meters) using ETDRS chart (SE)
- Tonometry and ophthalmologic examination (SE)

#### **Injection**

- 1st Injection - Randomized Treatment
  - Indirect Ophthalmoscopy (SE) – 1 to 2 minutes after the injection to assure that the optic nerve is perfused.

- Tonometry (SE) – After the injection, IOP must be  $\leq 21$  mmHg or within 5 mmHg of pre-injection before the 2nd injection can be given.
- 2nd Injection - Randomized Treatment

### **Post 2nd injection**

- Indirect Ophthalmoscopy (SE) – 1 to 2 minutes after the second injection to assure that the optic nerve is perfused.
- Ophthalmologic exam/Tonometry (SE) – At least 30 minutes after the second injection, a full ophthalmologic exam must be performed and IOP must be  $< 30$  mmHg before the subject leaves the clinic.

### **3-Day Post-Injection Safety Check ( $\pm 1$ day)**

- Telephone call to subject to ensure there are no signs or symptoms of retinal detachment or endophthalmitis.

### **10.2.24 Month 18 Visit ( $\pm 7$ days)/Early Withdrawal**

- Vital Signs
- Protocol refraction and visual acuity (4 meters) using ETDRS chart (OU)
- Tonometry and Ophthalmologic Examination (OU)
- Color fundus photography (FP) (OU)
- Fluorescein Angiography (FA) (OU, transit study eye)
- Spectral Domain Optical Coherence Tomography (SD-OCT) (OU)
- Fundus Autofluorescence (FAF) (OU)
- Microperimetry Testing (OU) (optional assessment)
- Serum pregnancy test (if applicable)
- Laboratory Tests
- 12-Lead ECG

### **10.3 Withdrawal from Trial**

Subjects have the right to withdraw from the trial at any time for any reason. The Investigator (after consultation with the Sponsor) or Sponsor also have the right to withdraw subjects from the trial in the event of concurrent illness, AEs, treatment-failure after a prescribed procedure, protocol violations, cure, administrative or other reasons.

Final trial assessments as outlined in the Study Assessments Chart, Section 3, should be performed on all subjects who withdraw. Subjects who withdraw due to an AEs

should be followed until resolution of the AEs, or an adequate explanation for the event is obtained.

Subjects who withdraw for any reason should have assessments performed according to the Early Withdrawal schedule. The subject must not receive an alternative treatment for Stargardt until he or she is withdrawn from the trial. If an alternative treatment for Stargardt is initiated before completing the study dosing, the subject will no longer be evaluated according to this protocol.

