#### **10.4 Trial Discontinuation**

The reason for a subject discontinuing from the trial will be recorded in the case report form (CRF). A discontinuation occurs when an enrolled subject ceases participation in the trial, regardless of the circumstances, prior to completion of the protocol. The investigator must determine the primary reason for discontinuation. A discontinuation must be reported immediately to the clinical monitor or his/her designated representative if it is due to a serious adverse reaction (SAE; see Section 12.3). The final evaluation required by the protocol will be performed at the time of trial discontinuation. The investigator will record the reason for trial discontinuation, provide or arrange for appropriate follow-up (if required) for such subjects, and document the course of the subject's condition.

Premature termination of this clinical trial may occur because of a regulatory authority decision, change in opinion of the IRB/EC, drug safety problems, or at the discretion of Astellas.

The study will be considered completed when the last subject completes the final study visit.

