#### **11.4.3 Statistical Analyses**

All statistical analyses will be conducted by the study Sponsor or under the authority of the study Sponsor. The Sponsor and the subjects will remain masked to treatments until the end of the study, except if safety considerations justify breaking the code for individual subjects.

Primary endpoint will be analyzed using a mixed model for repeated measures (MMRM) with all available data, using response variable of the area of ellipsoid zone defect measured by en face SD-OCT over time up to Month 18 including baseline and post-baseline assessments. The MMRM will be used to assess the difference between the treatment groups in terms of the rate of change (slope) in the area of ellipsoid zone defect from Baseline through Month 18. The fixed effects will include treatment group (avacincaptad pegol or Sham), time, pooled geographic region (North America or Rest of World) and treatment by time interaction. Subject is the random effect with repeated measures.

The efficacy analysis will be conducted on all randomized subjects according to the intention-to-treat principle.

A Statistical Analysis Plan (SAP) will provide the details for the statistical analyses.

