4.3 Primary Endpoint Analysis

4.3.1 Primary Estimand

The primary objective is to assess efficacy of ACP versus Sham in reducing the rate of change in the area of ellipsoid zone defect measured by en face SD-OCT from Baseline through Month 18 in participants with STGD1.

The following 5 attributes define the primary estimand for the primary objective evaluation:

1. Population: Participants with STGD1 that satisfy the inclusion/exclusion criteria specified in the protocol. The analysis will be performed in the ITT population.
2. Interventions: ACP versus Sham.
3. Variable: The area of ellipsoid zone defect (mm²) measured by en face SD-OCT from Baseline through Month 18.
4. Intercurrent events (ICE's) and strategies:
 - a. Study drug discontinuation: A hypothetical strategy will be adopted, as if all participants would continue treatment.
 - b. Any other interruption or change to treatment that does not result in study drug discontinuation: A treatment policy strategy will be adopted, i.e., all data pre and post ICE will contribute to the analysis.

- c. COVID-19: A treatment policy strategy will be adopted, i.e., all data pre and post ICE will contribute to the analysis.
5. Population-level summary: Difference between ACP group and Sham group in rate of change in the area of ellipsoid zone defect measured by en face SD-OCT from Baseline through Month 18.

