4.3.3 Supplementary Analysis: Jump to Reference Multiple Imputation

A supplementary analysis will be performed to estimate a slight modification of the Primary Estimand in Section 4.3.1, where instead of the hypothetical strategy, the treatment policy strategy is specified for the ICE of study drug discontinuation. To estimate this estimand, missing outcome data will be imputed using Jump to reference (J2R) multiple imputation (MI) under a missing not at random assumption. J2R MI will result in multiple data sets with complete outcome data. Then, the MMRM model described in Section 4.3.2 will be used to estimate the treatment effect in the multiple imputed data sets. Finally, Rubin's combination rules will be used to obtain a single estimate of the treatment effect and corresponding standard error.

It is worth noting that Rubin's rules can provide conservative inferences (Seaman et al. 2014, Bartlett 2021), e.g., CIs may have significantly greater than 95% coverage probability.

Therefore, jackknife resampling (Wolbers et al. 2022) may also be applied to obtain more accurate frequentist inferences.

The J2R assumption stipulates that the mean outcome trajectory in participants who discontinue study drug in the ACP group will follow the mean outcome trajectory of the Sham group, after the point of discontinuation. This J2R assumption will be used to impute missing outcome data for participants in the ACP group post study drug discontinuation. For participants in the Sham group at all time points and participants in the ACP group up to the time of study drug discontinuation, missing outcome data will be imputed under the missing at random assumption (MAR). The overall MI analysis will be implemented as follows:

1. Parameter estimation model: Let \mathbf{Y}_{Oi} denote the vector of all observed data, and \mathbf{Y}_{Mi} denote the vector of missing observations after the time point of the ICE (denoted by D_i), for participant i .
 - 1) Fit a multivariate normal (MVN) model using \mathbf{Y}_{Oi} , assuming MAR, to data up to the occurrence of the ICE. The MVN model will include pooled geographic region, treatment group, visit (categorical variable), and treatment-visit interaction in the mean function and have a common unstructured variance-covariance matrix across treatment groups.
 - 2) Draw a mean vector and a covariance matrix from the posterior distribution of the fitted MVN model parameters.

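### Protocol 10.3 lets removal on undefined grounds end follow-up as well as treatment, so the treatment-policy analyses must impute data that could have been collected

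*Protocol*

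**What the plan says.** Under Protocol 10.3 the investigator (after consulting the sponsor) or the sponsor may "withdraw subjects from the trial in the event of concurrent illness, AEs, treatment-failure after a prescribed procedure, protocol violations, cure, administrative or other reasons". Treatment failure and cure are not defined, and the list ends with an open category.

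On other treatment, the section says: "The subject must not receive an alternative treatment for Stargardt until he or she is withdrawn from the trial". It adds: "If an alternative treatment for Stargardt is initiated before completing the study dosing, the subject will no longer be evaluated according to this protocol".

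What is collected at exit is one visit: "Subjects who withdraw for any reason should have assessments performed according to the Early Withdrawal schedule". Section 10.2.24 shows that this visit includes SD-OCT, FAF and visual acuity. Beyond it, only follow-up of adverse events is required.

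Section 10.4 defines a single kind of discontinuation: "A discontinuation occurs when an enrolled subject ceases participation in the trial, regardless of the circumstances, prior to completion of the protocol". It describes no status of being off study drug but still followed.

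On analysis, Protocol 11.4.3 says: "The efficacy analysis will be conducted on all randomized subjects according to the intention-to-treat principle". The primary estimand (SAP 4.3.1) reads: "Study drug discontinuation: A hypothetical strategy will be adopted, as if all participants would continue treatment". In the supplementary analysis of SAP 4.3.3, "the treatment policy strategy is specified for the ICE of study drug discontinuation", with missing values imputed by jump to reference. SAP 4.4.3 does the same for the secondary endpoints. The intercurrent events in SAP 4.3.1 do not include starting another Stargardt treatment.

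**The concern.** A treatment-policy estimand asks what happens to everyone randomized, whatever treatment they go on to receive. It needs data collected after treatment stops. Protocol 10.3 allows those data to be lost by decision of the investigator or sponsor, although Protocol sections 6, 9.2.2 and 11.1 promise all subjects a final Month 18 visit.

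Two things are at stake.

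- **Supplementary analyses.** SAP 4.3.3 imputes Sham values under missing at random at all time points. ACP values after drug discontinuation follow the Sham trajectory, which is itself estimated from the Sham data that remain. If faster progressors leave Sham, jump to reference does not correct for it.
- **Primary slope.** The mixed model of SAP 4.3.2 is valid under missing at random given the ellipsoid-zone areas it contains. If a removal decision drew on information outside that model, such as monthly acuity or examination findings, that condition could fail. The sample size was set by feasibility, with no stated allowance for dropout (Protocol 11.3.1).

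**Working it through.** **1. The plan's scale.** With 60 per arm, the standard error of a difference in SD units is √(2/60) = 0.1826. Then 1.96 × 0.1826 = 0.358, which reproduces the protocol's 0.3577 SD significance cut-off (z = 1.959, one-sided p = 0.0250). The lower cut-off, 0.1843 SD, is z = 1.009. No SD and no withdrawal rate are given, so everything below is in SD units with assumed removal rates.

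**2. Does the Early Withdrawal scan reach the model?** The passages leave this open.
- Protocol section 7 says the reading center analyzes Screening, Month 9 and Month 18. Early Withdrawal is not named.
- SAP 4.3.2 uses areas at each scheduled visit, with time as actual study day.
- SAP 4.10.1 windows all visits. For SD-OCT, days 2–411 are Month 9 and day 412 onward is Month 18. Among competing visits, the one closest to the scheduled day (274 or 548) is used.

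So a withdrawal scan before Month 9 can enter if it is read. One taken between Month 9 and day 411 would normally lose to the Month 9 scan.

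**3. Extreme bound.** Remove the fastest fraction p of one arm only, ranked on true slope, with no post-baseline scan. With normal slopes, that arm's mean shifts by φ(z)/(1 − p):
- p = 0.05: 0.103/0.95 = 0.109 SD
- p = 0.10: 0.1755/0.90 = 0.195 SD

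**4. A common masked rule.** Assume a true effect of −0.50 SD, slope SD 1, and a removal signal equal to true slope plus noise of SD 0.5, so its correlation with slope is 1/√1.25 = 0.894. One cut-off applies to both arms, and removed participants contribute only a baseline scan. For 10% of Sham removed:
- Sham: z = 1.282; shift 0.894 × 0.1755/0.90 = 0.174
- ACP: z = 1.282 + 0.5 × 0.894 = 1.729, so 4.2% are removed; shift 0.894 × 0.0895/0.958 = 0.084
- Estimate: −0.50 + 0.174 − 0.084 = −0.41

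**5. Simulation of the same set-up.** Random intercept and slope, 40,000 per arm, scans at 0, 9 and 18 months, scan noise SD 0.15. Monte Carlo error is about √(2/40,000) = 0.007. Without removal the estimate is −0.506.

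| Removal pattern | 10% of Sham | 20% | 30% |
|---|---|---|---|
| Triggered by the modeled Month 9 scan | −0.505 | −0.496 | −0.513 |
| After Month 9, unread signal, no withdrawal scan | −0.485 | −0.482 | −0.497 |
| Same, with a Month 12 withdrawal scan modeled | −0.494 | −0.491 | −0.505 |
| Before Month 9, no withdrawal scan | −0.406 | −0.360 | −0.322 |

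Under the common rule ACP loses about 4%, 10% and 16%. With no true effect, every pattern gave an estimate within 0.013 SD of zero.

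**6. Effect of modeling the withdrawal scan.** For removal at Month 6 of 10% of Sham, with scan noise SD 0.3–0.6 and the withdrawal scan modeled, the estimate is −0.42 to −0.45 if removal tracks true slope perfectly, and about −0.48 if the removal signal correlates 0.5 with slope. For comparison, the formula in step 4 with perfect tracking and no scan gives −0.50 + 0.195 − 0.085 = −0.39. The scan recovers part of the loss.

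**The case against.** The case on the other side is substantial, and several stronger readings fail.

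- **Treatment failure means progression.** A reader might infer this because the disease is progressive and has no approved treatment. The documents do not say it. The term is undefined, is tied to a prescribed procedure, and appears in a generic list of discretionary grounds. Nothing says it would be judged on vision or lesion growth.
- **Removing protocol violators contradicts intention to treat.** It does not. Protocol 11.4.3 and SAP 3.1 keep everyone randomized in the analysis as assigned. Lost follow-up creates missing data, not exclusion. Nor is a protocol violation an outcome.
- **The bias is 0.195 SD, above the 0.1843 SD cut-off.** That bound needs removal from one arm only, perfect knowledge of slope and no withdrawal scan. Participants, assessors and sponsor are masked, a withdrawal scan is requested, and Protocol 11.3.1 calls the cut-offs guidelines.
- **The effect could be inflated.** This would need faster progressors to leave ACP more often. The documents offer no mechanism under masking; a common rule shrinks a real effect.

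It is also true that the primary estimand is hypothetical for drug discontinuation, so later off-drug scans are not its target. The alternative-treatment route is narrow, since no treatment is approved (Protocol 4.1) and 9.3 bars concomitant Stargardt treatment. SAP 4.2.1 counts discontinuation of treatment and of study separately, which suggests that the distinction was intended.

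What stands is that Protocol 10.3 and 10.4 do not provide for off-drug follow-up, and the handling of withdrawal scans is unsettled.

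**Conclusion.** The concern holds as a gap in data collection with a possible, unmeasured bias. Removal under 10.3 can end follow-up, so the treatment-policy analyses impute values that scheduled visits could have supplied.

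The effect on the primary slope depends on timing and on the withdrawal scan. Under a common masked rule, an assumed −0.50 SD effect falls to about −0.41 at 10% of Sham removed before Month 9 with no withdrawal scan modeled, and to −0.32 at 30%. It stays near −0.50 if removal follows Month 9, and no bias appears when there is no true effect. The demonstrated risk is therefore attenuation of a real effect, not a false positive. These figures rest on normal slopes, assumed removal rates and an assumed link between removal and progression. The documents neither establish nor exclude that link.

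**What to change.** 1. **Protocol 10.3 and 10.4:** separate stopping study treatment from leaving follow-up. State that withdrawal initiated by the sponsor or investigator, on any ground including the administrative and other category, does not end the Month 9 and Month 18 SD-OCT, FAF and BCVA assessments unless consent is withdrawn. Deleting individual grounds would not be enough, because the open category would still permit the same removals.
2. **SAP 4.3.3 and 4.4.3:** use the values so collected that belong to each endpoint in the treatment-policy analyses, and impute only what is still missing.
3. **Protocol section 7 and SAP 4.3.2 and 4.10.1:** state that Early Withdrawal scans are read by the reading center and enter the model at their actual study day, even when a Month 9 scan falls in the same window.
4. **Alternative treatment:** reconcile the sentence in 10.3 with Protocol 9.3 and with the intercurrent events in SAP 4.3.1. This concerns data collection and analysis and sets no treatment rule.
5. **Participants who have already finished:** Amendment C is dated March 2025, so new retention wording may come too late for many. The scan-reading rule and a table of withdrawal reasons by arm can still be specified before unmasking.

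The cost is a wording change, some site effort to retain participants for visits already scheduled, and a few extra image reads.
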